## 10.3 **Curcumin and vitamin D3 pharmacokinetics**

The purpose of this study is to measure standard pharmacokinetic parameters of curcumin and vitamin D in blood in all study subjects. For subjects with CLL, this data will also be integrated with pharmacodynamic parameters described above to determine the relationship between circulating drug levels and effects on VDR, NF- $\kappa$ B, and bcl-2. The purpose of this analysis is exploratory/proof of concept.

## 10.3.1 Background

Despite the use of doses of curcumin as high as 8 g/d in humans, very little free curcumin is typically found in patient plasma samples (43, 94). Rather, curcumin is present in plasma in conjugated (glucuronide and sulfate) forms, thereby necessitating appropriate enzymatic hydrolysis of the plasma before detection of free curcumin (95).

#### 10.3.2. Rationale for Analysis

Pharmacokinetic analysis of free curcumin with mass spectroscopy in human plasma, post oral administration, after appropriate enzymatic hydrolysis of the plasma has performed and validated before by different investigators (32, 43, 94). Since there is little or no correlation between plasma levels and effect (32, 96), there is little utility in performing intensive pharmacokinetic analysis. Vitamin D3 25OH (25-hydroxycholecalciferol) levels will be measured by liquid chromatography tandem-mass spectrometry (97). Serum levels of 25hydroxycholecalciferol has been validated as reflective of whole-body vitamin D stores and are used clinically to define vitamin D adequacy, deficiency, and toxicity (98). As we don't know how curcumin influences vitamin D metabolism, and vice versa, will assess curcumin and 25-hydroxycholecalciferol levels in plasma before treatment, one week after treatment with curcumin and before starting vitamin D3, and 3 weeks after treatment with both agents. No adjustment in dose or stopping of vitamin D is planned based on vitamin D OH level for 3 reasons: (1) The assay used to monitor vitamin D level is for research purposes and isn't a CLIA-certified assay; (2) We are not running samples in real time to make such clinical decisions; samples will be batch-assayed; (3) There is very little correlation between vitamin D levels and actual toxicity. Vitamin D toxicity is a clinical diagnosis and a normal serum calcium level excludes the diagnosis of vitamin D toxicity (please refer to section 8.1.1 for further details).

#### 10.3.3 Collection of Specimens

About 4-5 ml of blood will be drawn into 1 green-topped tube (containing heparin). The tube will be kept at ambient temperature and will be delivered to the TRPC laboratory within 3 hours of venipuncture. Blood samples will be drawn at the following 3 times points:

1.	Cycle 1, Day 1:	pre treatment
2.	Cycle 1, Day 8:	prior to starting vitamin D3
3	Cycle 2 Day 1.	after treatment with both curcumin and vi

#### 3. Cycle 2, Day 1: after treatment with both curcumin and vitamin D3

#### 10.3.4 Handling of Specimens

All specimens are to be shipped to the TRPC at the address below.

#### **Translational Research & Pharmacology Core**

ATTN [name] University Hospitals of Cleveland [name] [contact] [contact] [name] E-mail: [contact]

TRPC Personnel will log the specimen information into the OnCore database and de-identify the specimen using a code specific for this trial. CASE **5913** 38 of 74 Protocol Version 7 Dated **10/2/2018**  Plasma will be isolated by standard methods, aliquoted into cryovials (0.5ml/tube) and frozen at -70 C until analysis.

Specimens will be transported to the Case Comprehensive Cancer Center Pharmacology Core Facility Laboratory for analysis upon request of the Principle Investigator.

## If the sample is collected at an outside laboratory then it should be transported at room temperature as soon as possible to the TRPC by the rapid hospital courier service.

#### 10.3.5 Analytical Laboratory

All pharmacokinetic studies will be performed by the Case Comprehensive Cancer Center Pharmacology Core Facility Laboratory. Pharmacokinetic analysis of free curcumin with mass spectroscopy in human plasma, post oral administration, after appropriate enzymatic hydrolysis of the plasma has performed and validated before by different investigators (32, 43, 94). The Case Comprehensive Cancer Center Pharmacology Core Facility Laboratory has already developed, and validated, a method for analysis of 25-hydroxycholecalciferol (*[name]. personal communication*)

The Case Cancer Pharmacology Core [name] Contact: [name] Ph.D. [contact] Email: [contact]

#### 10.4 **Quality of Life Assessments**

The purpose of this correlative study is to measure the impact of curcumin and curcumin/vitamin D combination on quality of life (QOL) of patients with early stage CLL.

#### 10.4.1 Background and Rationale

Shanafelt et al. has demonstrated that CLL, at all stages, has a negative impact on QOL; the emotional well-being scores of CLL patients were dramatically lower than that of both the general population and patients with other types of cancer in analysis of 1482 patients (99). There is no intervention that has been shown to improve QOL in CLL patients. There is anecdotal evidence that curcumin and vitamin D improve QOL in cancer patients (100-103). Patients enrolled on the trial so far have reported improvement in their fatigue and overall sense of well-being.

#### 10.4.2 Measurement

We propose using the Functional assessment of chronic illness therapy- Lymphoma (FACT-Lym) questionnaire to assess QOL at baseline (within 2 weeks before starting C1 D1) and at end of treatment (within 2 weeks of discontinuation of study medication). Patients who are responding and will go on the 2 year continuation phase will take the FACT-Lym questionnaire within 2 weeks before starting C7 D1 and at the end of treatment. The FACT-Lym (appendix G) is a short, well-validated QOL measure has a general module (FACT-G) CASE **5913** 39 of 74 Protocol Version 7 Dated **10/2/2018**  with four subscales: physical, social/family, emotional and functional (104). The FACT-Lym was validated in indolent non-Hodgkin's lymphoma (which has a biology similar to CLL/SLL) and in CLL (105). Each of the four different subscales will be analyzed individually and the composite scale with 10% improvement after treatment considered significant based on prior published literature (106)

#### 10.5 Additional Correlative Studies

Study has been closed to accrual on 4/12/2016 at University Hospitals. Frozen plasma/serum and peripheral blood mononuclear cells will be shipped to [name] at the Ohio State University, former PI on the trial, to undertake further analysis of inflammatory cytokines and exosomes, under a material transfer agreement (MTA). [name] will have no access to patient identifying information and the generated research data set will be linked to clinical dataset through a unique patient number. They key linking datasets will be maintained at University Hospitals. The planned studies do not include any genetic analysis. Samples would be shipped to:

Leukemia Tissue Bank Shared Resource [name]

## 11.0 STUDY PARAMETERS AND CALENDAR

#### 11.1 **Study Parameters**

#### 11.1.1 Screening Evaluation

Screening studies and evaluations will be used to determine the eligibility of each subject for study inclusion. All evaluations must be completed  $\leq$  30 days prior to administration of protocol therapy. Bone marrow biopsy, flow cytometry, cytoegenetics, and interphase FISH performed up to 5 years prior to enrollment are acceptable.

- Informed Consent
- Demographics
- Medical History
- Complete physical examination including lymph node measurements (all palpable lymph nodes will be measured in greatest dimension and documented)
- Height
- Weight
- Vital signs including: blood pressure, pulse, temperature, and respiratory rate
- Concomitant Medications Assessment including prescription medications, OTC, and nutritional/herbal supplements.
- ECOG Performance status  $\leq 2$
- Baseline Symptoms Assessment
- Laboratory Studies:

- Complete Blood Count (CBC) with differential and platelets. Absolute lymphocyte count (ALC) will be calculated from CBC and differential
- Serum Chemistries: albumin, alkaline phosphatase, total bilirubin, bicarbonate, BUN, calcium, chloride, creatinine, glucose, potassium, total protein, SGOT [AST], SGPT [ALT], sodium
- Vitamin D 25(OH) level; standard of care test (63).
- Calculated creatinine clearance will be done if creatinine and/or BUN are abnormal.
- ß-HCG for women of childbearing potential
- CT scan of chest, abdomen, and pelvis (with and without contrast) will be performed in subjects with SLL who don't have ALC<5000 and non-measurable peripheral adenopathy. MRI may be performed if subject has allergy to iodinated contrast media
- Bone Marrow Biopsy is **optional** and not required prior to enrollment in study
- Peripheral blood flow cytometry (unless already performed on bone marrow biopsy)
- Peripheral blood cytogenetics including interphase FISH analysis for chromosome 11, 12, 13, and 17 abnormalities (unless already performed on bone marrow biopsy)

## 11.1.2 Treatment Period

Treatment cycles are 28 days long.

A visit window of  $\pm$  3 days is allowed for chemistry and hematology labs

A visit window of  $\pm$  7 days is allowed for 3 month and long term follow-up visits.

A visit window of  $\pm$  3 days is allowed for physical exams.

## Cycle 1, Day 1

Cycle 1, Day 1 evaluations do not need to be repeated if screening evaluations were conducted within 2 weeks prior to administration of protocol therapy.

- Physical Examination including lymph node measurements (all palpable lymph nodes will be measured in greatest dimension and documented)
- Weight
- Vital signs including: blood pressure, pulse, temperature, and respiratory rate
- Concomitant Medications Assessment including prescription medications, OTC, and nutritional/herbal supplements.
- ECOG Performance status  $\leq 2$
- Baseline Symptoms Assessment
- Laboratory Studies:
  - Complete Blood Count (CBC) with differential and platelets. ALC will be calculated from CBC and differential
  - Serum Chemistries: albumin, alkaline phosphatase, total bilirubin, bicarbonate, BUN, calcium, chloride, creatinine, glucose, potassium, total protein, SGOT [AST], SGPT [ALT], sodium
  - Calculated creatinine clearance will be done if creatinine and/or BUN are abnormal.
  - ο β-HCG for women of childbearing potential
  - Vitamin D 25(OH) level.

CASE **5913** Protocol Version 7 Dated **10/2/2018** 

## • Correlative Studies:

- Vitamin D receptor (VDR); by flow cytometry (only in subjects with CLL)
- $\circ$  NF- $\kappa$ B; by flow cytometry (only in subjects with CLL)
- bcl-2; by flow cytometry (only in subjects with CLL)
- Curcumin and vitamin D 25(OH) plasma level [PK]
- Curcumin dispensed to start on Day 1
- Pill diary distributed on Day 1

## Cycle 1, Day 8

- Weight
- Vital signs including: blood pressure, pulse, temperature, and respiratory rate
- ECOG Performance status  $\leq 2$
- Adverse events assessment
- Laboratory Studies:
  - Complete Blood Count (CBC) with differential and platelets. ALC will be calculated from CBC and differential
  - Serum Chemistries: albumin, alkaline phosphatase, total bilirubin, bicarbonate, BUN, calcium, chloride, creatinine, glucose, potassium, total protein, SGOT [AST], SGPT [ALT], sodium
  - Calculated creatinine clearance will be done if creatinine and/or BUN are abnormal.
- Correlative Studies:
  - Vitamin D receptor (VDR); by flow cytometry (only in subjects with CLL)
  - $\circ$  NF-κB; by flow cytometry (only in subjects with CLL)
  - bcl-2; by flow cytometry (only in subjects with CLL)
  - Curcumin and vitamin D 25(OH) plasma level [PK]
- Vitamin D3 dispensed to start on Day 8

Cycle 2, Day 1

- Physical Examination including lymph node measurements (all palpable lymph nodes will be measured in greatest dimension and documented)
- Weight
- Vital signs including: blood pressure, pulse, temperature, and respiratory rate
- Concomitant Medications Assessment including prescription medications, OTC, and nutritional/herbal supplements.
- ECOG Performance status  $\leq 2$
- Adverse events assessment
- Laboratory Studies:
  - Complete Blood Count (CBC) with differential and platelets. ALC will be calculated from CBC and differential
  - Serum Chemistries: albumin, alkaline phosphatase, total bilirubin, bicarbonate, BUN, calcium, chloride, creatinine, glucose, potassium, total protein, SGOT [AST], SGPT [ALT], sodium

- Vitamin D 25(OH) level (as clinically indicated if there are signs of vitamin D toxicity or if calcium level, corrected to serum albumin, is >11 mg/dL)
- Calculated creatinine clearance will be done if creatinine and/or BUN are abnormal.
- Correlative Studies:
  - Vitamin D receptor (VDR); by flow cytometry (only in subjects with CLL)
  - $\circ$  NF-κB; by flow cytometry (only in subjects with CLL)
  - bcl-2; by flow cytometry (only in subjects with CLL)
  - Curcumin and vitamin D 25(OH) plasma level [PK]
- Curcumin and vitamin D3 [4 week supply dispensed to start on Day 1]
- Pill diary collected and new diary distributed

Cycles 3-6, Day 1

- Physical Examination including lymph node measurements (all palpable lymph nodes will be measured in greatest dimension and documented)
- Weight
- Vital signs including: blood pressure, pulse, temperature, and respiratory rate
- Concomitant Medications Assessment including prescription medications, OTC, and nutritional/herbal supplements.
- ECOG Performance status  $\leq 2$
- Adverse events assessment
- On cycle 3 D1 only (+/- 3 days for flexibility of scheduling): CT scan of chest, abdomen, and pelvis (with and without contrast) will be performed in subjects with SLL who don't have ALC<5000 and non-measurable peripheral adenopathy. MRI may be performed if subject has allergy to iodinated contrast media. Purpose of this study is to assess response to treatment.
- Laboratory Studies:
  - Complete Blood Count (CBC) with differential and platelets. ALC will be calculated from CBC and differential
  - Serum Chemistries: albumin, alkaline phosphatase, total bilirubin, bicarbonate, BUN, calcium, chloride, creatinine, glucose, potassium, total protein, SGOT [AST], SGPT [ALT], sodium
  - Calculated creatinine clearance will be done if creatinine and/or BUN are abnormal.
  - Vitamin D 25(OH) level (as clinically indicated if there are signs of vitamin D toxicity or if calcium level, corrected to serum albumin, is >11 mg/dL)
- Curcumin and vitamin D3 [4 week supply dispensed to start on Day 1]
- Pill diary collected and new diary distributed

Cycles  $\geq$ 7 up to 2 years, Day 1 (for patients attaining a partial response or better)

- Physical Examination including lymph node measurements (all palpable lymph nodes will be measured in greatest dimension and documented)
- Weight
- Vital signs including: blood pressure, pulse, temperature, and respiratory rate

- Concomitant Medications Assessment including prescription medications, OTC, and nutritional/herbal supplements.
- ECOG Performance status  $\leq 2$
- Adverse events assessment
- Laboratory Studies:
  - Complete Blood Count (CBC) with differential and platelets. ALC will be calculated from CBC and differential
  - Serum Chemistries: albumin, alkaline phosphatase, total bilirubin, bicarbonate, BUN, calcium, chloride, creatinine, glucose, potassium, total protein, SGOT [AST], SGPT [ALT], sodium
  - Vitamin D 25(OH) level (as clinically indicated if there are signs of vitamin D toxicity or if calcium level, corrected to serum albumin, is >11 mg/dL)
  - Calculated creatinine clearance will be done if creatinine and/or BUN are abnormal.
- Curcumin and vitamin D3 [4 week supply dispensed to start on Day 1]
- Pill diary collected and new diary distributed

End of Treatment Visit (within 1 week of discontinuation of study medications)

- Physical Examination including lymph node measurements (all palpable lymph nodes will be measured in greatest dimension and documented)
- Weight
- Vital signs including: blood pressure, pulse, temperature, and respiratory rate
- Concomitant Medications Assessment including prescription medications, OTC, and nutritional/herbal supplements.
- ECOG Performance status  $\leq 2$
- Adverse events assessment
- Pill diary collected
- Laboratory Studies:
  - Complete Blood Count (CBC) with differential and platelets. ALC will be calculated from CBC and differential
  - Serum Chemistries: albumin, alkaline phosphatase, total bilirubin, bicarbonate, BUN, calcium, chloride, creatinine, glucose, potassium, total protein, SGOT [AST], SGPT [ALT], sodium
  - Calculated creatinine clearance will be done if creatinine and/or BUN are abnormal.
  - o β-HCG for women of childbearing potential
  - Vitamin D 25(OH) level (as clinically indicated if there are signs of vitamin D toxicity or if calcium level, corrected to serum albumin, is >11 mg/dL)

## 30 Day Follow-Up

- Physical Examination including lymph node measurements (all palpable lymph nodes will be measured in greatest dimension and documented)
- Weight
- Vital signs including: blood pressure, pulse, temperature, and respiratory rate

- Concomitant Medications Assessment including prescription medications, OTC, and nutritional/herbal supplements.
- ECOG Performance status  $\leq 2$
- Adverse events assessment
- Laboratory Studies:
  - Complete Blood Count (CBC) with differential and platelets. ALC will be calculated from CBC and differential
  - Serum Chemistries: albumin, alkaline phosphatase, total bilirubin, bicarbonate, BUN, calcium, chloride, creatinine, glucose, potassium, total protein, SGOT [AST], SGPT [ALT], sodium
  - Calculated creatinine clearance will be done if creatinine and/or BUN are abnormal.
  - Vitamin D 25(OH) level (as clinically indicated if there are signs of vitamin D toxicity or if calcium level, corrected to serum albumin, is >11 mg/dL)

# Long Term Follow-Up (for 2 years after discontinuation of study medications, every 3-6 months as clinically indicated)

- Physical Examination including lymph node measurements (all palpable lymph nodes will be measured in greatest dimension and documented)
- Weight
- Vital signs including: blood pressure, pulse, temperature, and respiratory rate
- ECOG Performance status  $\leq 2$
- Adverse Events Assessment
- Laboratory Studies:
  - Complete Blood Count (CBC) with differential and platelets
  - Serum Chemistries: albumin, alkaline phosphatase, total bilirubin, bicarbonate, BUN, calcium, chloride, creatinine, glucose, potassium, total protein, SGOT [AST], SGPT [ALT], sodium
  - Calculated creatinine clearance will be done if creatinine and/or BUN are abnormal.

## 11.2 Calendar

Screening studies will studies are to be conducted within 30 days prior to administration of protocol therapy. Exception: Bone marrow biopsy, flow cytometry, cytometry, cytoegenetics, and interphase FISH performed up to 5 years prior to enrollment

Study Days	Pre- Study	Cycle 1 Day 1 b	Cycle 1 Day 8	Cycle 2 Day 1	Cycles 3- 6 Day 1	Cycles 7+ Day 1 f	End of Treatment	30 Day Follow Up i	Long term Follow- Up g,i
REQUIRED ASSESSMENTS									

r				1	1				
Informed Consent	Х								
Demographics	Х								
Medical History	Х								
Height	Х								
Weight	Х	Х	Х	Х	Х	Х	Х	Х	Х
Vitals (blood pressure,	Х	Х	Х	Х	Х	Х	Х	Х	Х
pulse, temperature, and									
respiratory rate)									
Physical Examination i	Х	Х		X	Х	Х	Х	Х	Х
Concomitant	Х	X		X	X	Х	Х	Х	
Medication									
Assessment									
ECOG PS	Х	X	X	X	X	Х	Х	Х	Х
Baseline Symptoms	Х	X							
Adverse Event			X	X	X	X	X	X	X
Assessment									
Peripheral blood flow	X								
cvtometry									
Peripheral blood	X								
cytogenetics and FISH									
CBC / diff / platelets i	X	X	X	X	X	X	X	X	Х
Serum Chemistry a, i	X	X	X	X	X	X	X	X	X
B-HCG women of	X	X					X		
childbearing potential									
Vitamin D 25(OH)	X	X*		X*	X*	X*	X*	X	
level									
DISEASE									
ASSESSMENT									
Lymph node	Х	X		X	X	Х	Х	Х	Х
measurement									
СТ	Х				Х				
chest/abdomen/pelvis c									
Bone marrow biopsy	Х								
(optional)									
MISC ITEMS									
Pill Diary		Х		X	X	X	Х		
TREATMENT									
Curcumin									
Vitamin D3									
CORRELATIVE									
STUDIES									
Pharmacokinetic		X	X	X					
Sampling d									
Flow cytometry e		Х	Х	X					
Ouality of life	X h	1		1	1	1	X h		
questionnaire									

**a:** Albumin, alkaline phosphatase, total bilirubin, bicarbonate, BUN, calcium, chloride, creatinine, glucose, potassium, total protein, SGOT [AST], SGPT [ALT], sodium. Calculated creatinine clearance will be done if creatinine and/or BUN are abnormal. **[UH: Order COMP2]** 

**b:** Cycle 1, Day 1 evaluations do not need to be repeated if screening evaluations were conducted within 2 weeks prior to administration of protocol therapy

c: In subjects with SLL who have ALC<5000 and non-measurable peripheral adenopathy

**d:** Plasma level of curcumin and vitamin D 25(OH)

e: For vitamin D receptor, NF-κB, and bcl-2, CLL patients only

f: For patients attaining a partial response or better

g: Every 3-6 months as clinically indicated

**h**: Utilizing FACT-Lym questionnaire (appendix G) within 2 weeks prior to start of treatment and within 2 weeks of discontinuation of study medications. Patients who are responding and will go on the 2 year continuation phase will take the FACT-Lym questionnaire within 2 weeks before starting C7 D1 and at the end of treatment.

i. +/- 3 day window

\*: As clinically indicated if there are signs of vitamin D toxicity or if calcium level, corrected to serum albumin, is >11 mg/dL

## MEASUREMENT OF EFFECT

#### **12.1** Response Criteria for CLL; based on NCI-WG (107)

**Complete response** requires all of the following for a period of at least two months from completion of therapy:

- Peripheral blood lymphocytes (evaluated by blood and differential count) below 4 x 10^9/L (4000/\_L).
- Absence of significant lymphadenopathy (eg, lymph nodes >1.5 cm in diameter) by physical examination.
- No hepatomegaly or splenomegaly on physical exam;
- Absence of constitutional symptoms;
- Normal CBC as exhibited by polymorphonuclear leukocytes >  $1500/\mu$ L, platelets >  $100,000/\mu$ L, hemoglobin > 11.0 g/dl (untransfused)
- Bone marrow aspirate and biopsy must be at least normocellular for age, with less than 30% of nucleated cells being lymphocytes. Lymphoid nodules should be absent. If the marrow is hypocellular, a repeat determination should be performed after 4 weeks, or until peripheral blood counts have recovered. However, this time interval should not exceed 6 months after the last treatment.
- Patients who fulfill the criteria for CR after induction with the exception of a persistent cytopenia that is believed to be treatment related will be considered a partial response. Additionally, patients who fulfill the criteria of CR with exception of having bone marrow lymphoid nodules will be considered a partial response. Patients who fulfill the criteria of CR but declined having a bone marrow biopsy will be considered be in PR.

**Partial response** requires a > 50% decrease in peripheral lymphocyte count from pretreatment value, > 50% reduction in lymphadenopathy, and/or > 50% reduction in splenomegaly/ hepatomegaly for a period of at least two months from completion of therapy. All lymph nodes will be measured bi-dimensionally and the sums of these added to determine if 50% or greater reduction has occurred.

Additionally, these patients must have one of the following:

- Polymorphonuclear leukocytes > 1,500/µL or 50% improvement from pre-treatment value;
- Platelets >  $100,000/\mu$ L or 50% improvement from pre-treatment value;
- Hemoglobin > 11.0 g/dl (untransfused) or 50% improvement from pretreatment value.

**Progressive Disease** is characterized by any one of the following events:

- >50% increase in the products of at least two lymph nodes (at least one lymph node must be > 2 cm); appearance of new palpable lymph nodes.
- > 50% increase in the size of the liver and/or spleen as determined by measurement below the respective costal margin; appearance of palpable hepatomegaly or splenomegaly, which was not previously present.
- >50% increase in the absolute number of circulating lymphocytes to at least  $5,000/\mu$ L.
- Transformation to a more aggressive histology (i.e., Richter's syndrome or prolymphocytic leukemia with > 55% prolymphocytes).
- Patients not fulfilling the above criteria for progressive disease but demonstrating a decrease in hemoglobin > 2 gm/dl, decrease > 50% in platelet or granulocyte count will not be rated as progressive disease because these may occur as both a consequence of therapy and of underlying CLL. A bone marrow biopsy in such settings is strongly encouraged.

**Stable Disease** includes patients who do not fulfill the criteria for complete or partial response as defined above but do not exhibit progressive disease will be considered as having stable disease.

Parameter	CR*	PR*	PD*
Group A			
Lymphadenopathy†	None > 1.5 cm	Decrease ≥ 50%	Increase ≥ 50%
Hepatomegaly	None	Decrease ≥ 50%	Increase ≥ 50%
Splenomegaly	None	Decrease ≥ 50%	Increase ≥ 50%
Blood lymphocytes	< 4000/µL	Decrease ≥ 50% from baseline	Increase ≥ 50% over baseline
Marrow‡	Normocellular, < 30% lymphocytes, no B-lymphoid nodules. Hypocellular marrow defines CRi (5.1.6).	50% reduction in marrow infiltrate, or B-lymphoid nodules	
Group B			
Platelet count	$> 100 \ 000/\mu L$	$>100~000/\mu L$ or increase $\geq 50\%$ over baseline	Decrease of ≥ 50% from baseline secondary to CLL
Hemoglobin	> 11.0 g/dL	$>$ 11 g/dL or increase $\geq$ 50% over baseline	Decrease of > 2 g/dL from baseline secondary to CLL
Neutrophils‡	> 1500/µL	> 1500/µL or $>$ 50% improvement over baseline	

Group A criteria define the tumor load, group B criteria define the function of the hematopoietic system (or marrow).

\*CR (complete remission): all of the criteria have to be met, and patients have to lack disease-related constitutional symptoms; PR (partial remission): at least two of the criteria of group A plus one of the criteria of group B have to be met; SD is absence of progressive disease (PD) and failure to achieve at least a PR; PD: at least one of the above criteria of group A or group B has to be met.

†Sum of the products of multiple lymph nodes (as evaluated by CT scans in clinical trials, or by physical examination in general practice). ‡These parameters are irrelevant for some response categories.

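### Section 12.1 defines CLL response twice, in prose and in a table that disagree on PD and PR, with no stated precedence, and the visit lists order one node diameter where two are needed

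*Combined protocol and SAP*

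**What the plan says.** **PD.** In the prose of 12.1, a patient who meets no other PD criterion but has a hemoglobin fall above 2 g/dL, or a fall above 50% in platelets or granulocytes, "will not be rated as progressive disease because these may occur as both a consequence of therapy and of underlying CLL". It adds: "A bone marrow biopsy in such settings is strongly encouraged". In the table, the hemoglobin cell under PD reads "Decrease of > 2 g/dL from baseline secondary to CLL". The platelet cell is parallel, at a fall of 50% or more, and the footnote states "PD: at least one of the above criteria of group A or group B has to be met".

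**PR.** The prose lists falls above 50% in lymphocytes, in nodes and in spleen or liver, joined by *and/or*. They must hold for at least two months from completion of therapy, and one blood-count criterion is added. The table footnote requires that "at least two of the criteria of group A plus one of the criteria of group B have to be met". Its group A includes marrow ("50% reduction in marrow infiltrate, or B-lymphoid nodules"), and it gives no duration.

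**Nodes.** The PR prose orders bi-dimensional measurement, the PD prose uses products of node diameters, and the table uses the sum of products. Section 11.1 orders greatest dimension only, at screening, Cycle 1 Day 1, Cycle 2 Day 1, Cycles 3-6, Cycles 7 and later, end of treatment, 30-day and long-term follow-up. Cycle 1 Day 8 has no node measurement. CT is scheduled only for certain SLL subjects (11.2, footnote c).

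**Precedence.** Sections 2.1, 12.1 and 14 do not say whether the prose or the table decides.

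**The concern.** Section 14.4.2 requires one response category per patient and counts PD as treatment failure, so someone must choose between the two rule sets case by case. The trial is open label, so that choice would be made with outcomes in view. The labels have consequences: CR and PR make up the NCI-WG response rate in 2.1, PR or better opens therapy for up to two years (6.0), and PD stops treatment (6.3), ends response (12.5) and is a PFS event (12.6). Separately, if only one diameter is recorded, nodal PR and PD cannot be computed under either rule set.

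**Working it through.** No stated figure depends on this point, so the check sets the two texts side by side and then tests them on constructed patients. The documents give no frequencies; the cases show what is possible, not how common it is.

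**1. The two rule sets**

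| Item | Prose | Table and footnotes |
|---|---|---|
| Cytopenia alone, due to CLL | Not PD | PD (Hb or platelets) |
| Nodal PD | Above 50% rise in products of two or more nodes, one above 2 cm | Rise of 50% or more in sum of products |
| Lymphocyte PD | Above 50% rise, to at least 5,000/µL | Rise of 50% or more, no floor |
| New nodes, new organomegaly, transformation | PD | Not listed |
| PR count | *and/or*, number open | Two group A plus one group B |
| PR duration | Two months from completion of therapy | None |
| Node assessment | Physical examination named (CR) | CT in clinical trials |

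**2. PD by the table only**
- Two nodes from 1.6 × 1.6 to 2.0 × 2.0 cm: sum of products 2 × 1.6² = 5.12 to 2 × 2.0² = 8.00 cm²; 8.00/5.12 − 1 = +56%. No node exceeds 2 cm, so the prose does not call PD.
- Hemoglobin 13.0 to 10.8 g/dL, attributed to CLL: a fall of 2.2 g/dL.
- Lymphocytes 2,500 to 4,000/µL: +60%, below the prose floor. The floor matters only when the reference count is below 5,000/1.5 = 3,333/µL.

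**3. PD by the prose only**
- Two stable 2.0 × 2.0 cm nodes plus one new palpable 1.0 × 1.0 cm node: 8.00 to 9.00 cm², 9.00/8.00 − 1 = +12.5%. The new node is PD by the prose; the table threshold is not met.

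**4. PR or SD**
- Lymphocytes down 60% and held two months, nodes down 20%, no organomegaly, no marrow, hemoglobin 12 g/dL. With *and/or* read as *or*, this is PR by the prose. By the table it is SD (one group A criterion). It is a biologic response either way, because the 12.4 lymphocyte threshold is a fall above 20%.
- Each such relabel moves the CR+PR rate by 1/29 = 3.4 points, or 1/35 = 2.9 points.

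**5. One diameter against two**
- Greatest dimension 3.0 to 2.1 cm (−30%), with a starting perpendicular of 2.0 cm (product 6.0 cm²). If the perpendicular is unchanged, 2.1 × 2.0 = 4.2 cm², −30%. If it shrinks in proportion, 2.1 × 1.4 = 2.94 cm², −51%. The first is not a nodal PR; the second is.
- A node going from 4 × 3 to 4 × 1.4 cm loses 1 − 5.6/12 = 53% of its product with no change in greatest dimension.
- With constant shape, a 50% product fall is a diameter fall of 1 − √0.5 = 29.3%, and a 50% product rise is a diameter rise of √1.5 − 1 = 22.5%. A 50% cut-off applied to one diameter would be far stricter.

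**6. Design figures (14.2)**
- With 1/10 and 5/29 as the stopping and rejection limits, exact binomial calculation gives early termination 0.736 at P = 0.1, type I error 0.047 and power 0.805 at P = 0.3. The plan states 0.74, 0.05 and 0.8. They reproduce, and none depends on the PR or PD definition.

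**The case against.** The strongest reply is that the consequence is small. The endpoint in 14.1 and the stopping rule in 14.2 count biologic response, so the PR/SD patient above is a responder under both rule sets. PFS has no comparator arm, and the worked PD cases sit near thresholds: at 2.1 cm instead of 2.0 cm, the two nodal rules agree. This stands, and it limits the severity.

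The PR conflict also depends on wording: if *and/or* requires both lymphocytes and nodes, prose and table agree on SD in that case. True, but the prose does not say so, and the differences in duration and marrow remain on any reading. The table's attribution to CLL narrows the cytopenia conflict without removing it, since the prose excludes isolated cytopenia even where CLL is the cause.

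It can be argued that precedence is already settled, because the SD sentence before the table covers patients who "do not fulfill the criteria for complete or partial response as defined above". That points to the prose for CR and PR, but does not reach the PD rules, and the table footnote carries its own SD definition.

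On nodes, 12.1 does order two dimensions and 11.1 does not forbid a second one. A reader might infer that the second diameter was never recorded. The documents show no case report form for node measurements, so they support only the conflict between the instructions.

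**Conclusion.** The point holds as an inconsistency of definitions, of minor to moderate severity. Two stated rule sets can give the same CLL patient different PR/SD or SD/PD labels, in either direction. The effect falls on the CR+PR rate in 2.1, access to the extension, duration of response and PFS. How many patients are affected cannot be estimated from the documents.

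Two stronger readings are not supported. First, a reader might infer that the primary endpoint or the go/no-go decision is unreliable. A lymphocyte-based PR already exceeds the biologic threshold, so the composite moves little. The residual exceptions are a patient whose only qualifying change is in spleen or liver, and one who is PD under one rule set only. No power or sample-size figure changes.

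Second, a reader might infer that the table should govern because its counting rule is clearer. It has no PR duration and omits new lesions and transformation. It refers to CT, which CLL patients are not scheduled to have, and counts a marrow that the calendar lists only before study and as optional.

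**What to change.** In 12.1:
- State that the prose governs and that the table is for reference only.
- Replace *and/or* with an explicit count, for example two tumour-load criteria plus one blood-count criterion, and keep the requirement of two months from completion of therapy.
- State one rule for cytopenia attributed to CLL; following the prose, it is not PD on its own.
- Report CR+PR and PFS under the table rules as a sensitivity analysis.

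In 11.1, order two perpendicular diameters at any remaining visit, and flag nodal PR or PD calls that rest on one diameter. Leave the 12.4 biologic-response threshold alone: it is part of the primary endpoint, and accrual closed on 4/12/2016 (10.5).

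**Cost.** A few sentences and some reclassification of existing data. With therapy capped at two years and two years of follow-up, treatment should have ended by about April 2018 and follow-up by about April 2020, so new measurements can recover little. Under a two-criterion rule, a patient with lymphocytosis only who does not reach the CR limit of 4,000/µL has one evaluable criterion and cannot reach PR without a marrow result that counts, so both counts should be shown. The rule is being chosen late, after accrual closed, and the report should say so.
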